3. OBJECTIVES AND ENDPOINTS

Table 3: Study Objectives and Endpoints

| Objectives | Endpoints |
|---|--|
| Primary To characterize the safety and tolerability of lerociclib in combination with endocrine therapy in participants with 1L and 2L HR+/HER2- mBC | 
 Incidence of AEs and SAEs |
| Secondary To investigate the efficacy of lerociclib in combination with endocrine therapy in participants with 1L and 2L HR+/HER2- mBC by line of therapy | 
 Objective response rate, defined as the proportion of participants with a best overall response of CR or PR according to RECIST v1.1 as assessed by Investigator Clinical benefit rate, defined as the proportion of participants with a best overall response of CR, PR, or SD (for at least 8 weeks) according to RECIST v1.1 as assessed by Investigator Progression-free survival, defined as the time from first dose of lerociclib until the date of documented PD or death, according to RECIST v1.1 as assessed by Investigator Overall survival, defined as the time from the date of first dose of lerociclib to the date of death due to any cause Duration of response, defined as the time from the date of first documented response until the date of confirmed PD or death, according to RECIST v1.1 as assessed by Investigator Time to response, defined as the time from first dose of lerociclib until the first documented response (CR or PR) |
| To further characterize the safety and tolerability of lerociclib in combination with endocrine therapy in participants with 1L and 2L HR+/HER2- mBC | 
 Change from baseline in clinical laboratory parameters (hematology, clinical chemistry, coagulation, fasting lipid panel, and urinalysis) Change from baseline in vital signs and 12-lead ECG parameters |

Table 3: Study Objectives and Endpoints (Continued)

| Objectives | Endpoints |
|---|--|
| To assess change from baseline in global health status and QoL in participants with 1L and 2L HR+/HER2- mBC by line of therapy | 
 • Change from baseline in the Global Health Status/QoL Scale Score of the EORTC-QLQ-C30 • Change from baseline in the Global Health Status/QoL Scale Score of the EORTC-QLQ-BR23 • Change from baseline in the Global Health Status/QoL Scale Score of the EQ-5D-5L • Change from baseline in the Global Health Status/QoL Scale Score of the FACIT Item GP-5 |

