While receiving lerociclib, participants will undergo imaging assessments (via CT of the chest/abdomen/pelvis with contrast or MRI with gadolinium) every 8 weeks for the first 12 months, then every 12 weeks thereafter. All participants will undergo a bone scan at baseline and annually thereafter (or as per the Investigator's standard of care). If bone disease is identified, participants will require whole-body bone scans every 8 weeks for the first 12 months and then every 12 weeks thereafter.

Optional imaging modalities include a brain CT/MRI (if brain lesion[s] indicated at Screening), CT/MRI for any disease outside the chest/abdomen/pelvis (if lesion[s] identified at Screening), or skin color photography (if skin lesion[s] identified at Screening) every 8 weeks during the first 12 months, then every 12 weeks thereafter.

Participants will continue therapy until disease progression as determined by the Investigator per RECIST v 1.1, unacceptable toxicity, withdrawal of consent, start of a new anticancer treatment, discontinuation of the participant by the Investigator, or termination of the study by the Sponsor, whichever occurs first.

Following disease progression, participants will only be followed for survival, and will no longer require any scheduled assessments beyond that timepoint. Survival status will be assessed every 12 weeks regardless of the participant's reason for discontinuing study treatment.

Safety monitoring (AE/SAE monitoring, clinical laboratory tests, vital signs, 12-lead ECGs, physical examination), serial blood samples for PK, tumor biopsies, and bone scans will be performed at the timepoints specified in the study SoA ([Table 1](#)).

The study is anticipated to last for a total of approximately 48 months. This assumes 12 months to complete participant recruitment and a median PFS of 24 months, plus an additional 12 months for further monitoring.

An independent DSMB will be set up to periodically review and evaluate the accumulated study data for participant safety and for study conduct and progress, and to make recommendations to the Sponsor concerning the continuation of the study (as detailed in [Section 7.4](#)).

This study will be conducted in compliance with the protocol, GCP, and applicable regulatory and IRB/IEC requirements.

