8.1.1. Antitumor Activity Assessments

For tumor assessment, all sites of disease, including but not limited to the chest, abdomen, and pelvis, should be assessed radiologically by CT or MRI at Screening and every 8 weeks for the first 12 months, then every 12 weeks until the occurrence of disease progression ([Table 1](#)). A central imaging vendor will be used to collect and hold these images for possible future review by independent radiologists. Objective response data collected for the clinical study report will be based on Investigator assessment.

Scans (CT or MRI) obtained prior to informed consent will not need to be repeated if performed within 28 days prior to dosing. Radionuclide bone scans shall be performed at Screening for all participants and annually thereafter or as clinically indicated. All participants with a CR must have a radionuclide bone scan as part of confirmation of the CR. Additional scans may be obtained at the discretion of the Investigator, if clinically indicated.

Participants with bone-only disease will be followed with bone scans only at Screening and every 12 weeks on treatment.

If a participant shows a radiological response (CR or PR), a confirmatory radiological assessment will be performed at least 4 weeks after the response was first noted. Participants who have a confirmed CR will have a bone scan to confirm absence of bony metastases.

For all participants (1L or 2L populations), if they remain on therapy for 12 months following enrollment, the timing of CT or MRI scans should be lengthened to every 12 weeks.

The same method of assessment (CT or MRI) should be used to characterize tumors at Screening and at all follow-up assessments. If PET is used, it should also be accompanied by spiral CT or MRI.

Investigators should follow RECIST v1.1 Guidelines ([Eisenhauer 2009](#)) for tumor assessments and determination of overall response.

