4.10.2 RECIST Overall Response

The primary evaluation of efficacy endpoints will be based on the final assessment of timepoint Overall Response.

Extent of disease and tumor response will be assessed using Overall Response at each timepoint RECIST v1.1 ([Eisenhauer 2009](#)) as assessed by the Investigator (refer to Section 8.1.1 of the protocol). An Overall Response at each timepoint will be derived algorithmically based on the data entered for Target Lesions, Non-Target Lesions, and New Lesions. However, the Investigator can override this determination based on their clinical judgment of the participant at time of evaluation. In such cases the result of the RECIST algorithm will take precedence in the primary evaluation. The effect of any Investigator overrides will be explored as a sensitivity analysis.

. For participants with measurable disease at baseline the following timepoint responses are possible:

- Progressive Disease (PD)
- Stable Disease (SD)
- Partial Response (PR)
- Complete Response (CR)
- Not Evaluable (NE)

For participants who do not have measurable disease at baseline the following timepoint responses are possible:

- Progressive Disease (PD)
- Non-Complete Response / Non-Progressive Disease (Non-CR/Non-PD)
- Complete Response (CR)
- Not Evaluable (NE)

Once a RECIST v1.1 timepoint response of PD is observed all subsequent RECIST evaluations will not be used in analysis unless otherwise specified [REDACTED]

The primary evaluations of tumor response (ORR, CBR, DOR, and TTR) will be based on the RE set, which is limited to participants with measurable disease at baseline. [REDACTED]

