4.10.3.2 Progression-free Survival (PFS)

Progression-Free Survival (PFS) is defined as the time to PFS event from first exposure to lerociclib. PFS event is defined as PD (per RECIST v1.1 as assessed by the investigator) or death due to any cause, whichever comes first. For participants without death or disease progression, PFS will be censored at the date of the last valid RECIST assessment unless otherwise stated. PFS duration will be calculated as

$$\text{Date of observation} - \text{Date of first exposure to lerociclib} + 1$$

where date of observation is the earliest of death, progression, or censoring.

PFS events and censoring rules, such as initiation of disallowed anticancer therapy, are defined below in Table 2.

All valid RECIST assessments after start of treatment will be used in the PFS analysis regardless of whether they were collected as part of scheduled or unscheduled visits. RECIST assessments based on scans performed after the end of lerociclib therapy will be used in the analysis of PFS if prior censoring events have not been observed.

Table 2 Censoring Rules for Progression-Free Survival

| Situation | Outcome | Date of Event/ Censoring |
|--|---------|---|
| PD or death, whichever occurred first, before exposure to subsequent antineoplastic therapy, withdrawal of consent, loss to follow up, data cutoff, or end of study. | Event | Earliest date of documented progression or death |
| No baseline disease assessment | Censor | Date of first exposure |
| No valid post-baseline tumor assessment | Censor | Date of first exposure |
| PD or death immediately after missing ≥ 2 consecutive scheduled tumor assessment | Censor | Date of last valid tumor assessment prior to the missing tumor assessments |
| No PD or death on or before 
 Database cut End of study Start of new antineoplastic therapy | Censor | Date of last tumor assessment on or prior to earliest censoring event listed in first column of this row. |

Descriptive summaries of time to event data will include median, twenty-fifth and seventy-fifth percentiles, and associated 2-sided 95% CIs based on Kaplan-Meier methods. Survival estimates along with corresponding 95% CIs using the log-log transformation will be provided at certain intervals as data allows.

A Kaplan-Meier plot will be presented and will include the number of participants at risk over time by line of therapy. No formal statistical hypothesis will be tested.

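### SAP 4.10.2 lets a programmed RECIST result displace the Investigator's recorded response in the main efficacy analyses, against the endpoint definitions, and exposes Investigator-only progressions to informative censoring

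*SAP*

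**What the plan says.** SAP 4.10.2 begins: "The primary evaluation of efficacy endpoints will be based on the final assessment of timepoint Overall Response". The timepoint response is "derived algorithmically based on the data entered for Target Lesions, Non-Target Lesions, and New Lesions". The Investigator may override it on clinical judgment, but "In such cases the result of the RECIST algorithm will take precedence in the primary evaluation". The override is left to one further sentence: "The effect of any Investigator overrides will be explored as a sensitivity analysis". No endpoints, method or censoring rule are given for that analysis.

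The definitions name a different source. Protocol Section 3 defines PFS as "time from first dose of lerociclib until the date of documented PD or death, according to RECIST v1.1 as assessed by Investigator" and names the same assessor for ORR, CBR and DOR; SAP 3.2 repeats this. (TTR names no assessor but rests on the same responses.) SAP 4.10.3.2 states: "PFS event is defined as PD (per RECIST v1.1 as assessed by the investigator) or death due to any cause, whichever comes first". Protocol 8.1.1 states: "Objective response data collected for the clinical study report will be based on Investigator assessment".

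Follow-up also depends on the Investigator. Under Protocol 4.1, therapy runs until progression as the Investigator determines it, and then: "Following disease progression, participants will only be followed for survival, and will no longer require any scheduled assessments beyond that timepoint".

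In SAP 4.10.3.2, Table 2 censors a participant without PD or death at the last tumor assessment on or before the earliest of data cut, end of study or new antineoplastic therapy. It also censors back a PD or death that follows two or more consecutive missed assessments. DOR uses the same rules (SAP 4.10.3.4). SAP 4.13 reports no change to the protocol's statistical methods.

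**The concern.** There are two problems. First, SAP 4.10.2 and 4.10.3.2 can give different PFS dates for the same participant, so the reported endpoint depends on which section the programmer follows.

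Second, one source ends observation and another declares the event. The Investigator's call of progression stops treatment and scheduled imaging, but under SAP 4.10.2 that call does not count as a PFS event unless the program agrees. A participant can therefore leave the risk set because he or she was judged to be progressing. Kaplan-Meier estimation assumes that censored participants have the same outlook as those who remain, and here that assumption would fail.

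**Working it through.** **1. Whose response counts**

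| Place | Source |
|---|---|
| Protocol 3 and SAP 3.2 (ORR, CBR, PFS, DOR) | Investigator, under RECIST v1.1 |
| Protocol 8.1.1 | Investigator |
| SAP 4.10.3.2, PFS event | Investigator |
| Protocol 9.3.3.2 to 9.3.3.4 | RECIST v1.1, no assessor named |
| SAP 4.10.2, main evaluation | Program, where the two differ |

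**2. A participant with Investigator PD but no programmed PD**

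- Treatment ends and scheduled scans cease (Protocol 4.1).
- The extra scan at discontinuation in Protocol 7.1.1 is for participants who stop for reasons other than PD. The schedule of activities does list an EOT/ED tumor evaluation, as applicable, and SAP 4.10.3.2 uses scans after the end of lerociclib if no censoring event has come first. A programmed PD could still arise there.
- A death before new therapy still counts, unless it follows two or more missed assessments. The SAP does not say whether scans no longer required after Investigator PD count as missed.
- Otherwise Table 2 censors at the last assessment, which will usually be the scan on which the Investigator called progression.

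**3. The plan's own figure**

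The plan gives no figure for discordance. Its one precision statement is an ORR confidence-interval half-width of about 16% with 40 evaluable participants per line. Clopper-Pearson at 20/40 gives 33.8% to 66.2%, a half-width of 16.2%, so the figure reproduces. It does not depend on who assesses. Each reclassified responder moves ORR by 1/40 = 2.5 points.

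**4. Illustration for PFS**

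Inputs: the planning median of 24 months (Protocol 4.1), exponential PFS, and an assumed share q of events that are Investigator PDs not reproduced by the program, all censored at that time. The estimated hazard is multiplied by (1 − q), so the median is 24/(1 − q) and 24-month PFS is 0.5^(1 − q).

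| q (assumed) | Median, months | 24-month PFS |
|---|---|---|
| 0 | 24.0 | 50.0% |
| 5% | 24/0.95 = 25.3 | 51.8% |
| 10% | 24/0.90 = 26.7 | 53.6% |
| 15% | 24/0.85 = 28.2 | 55.5% |
| 20% | 24/0.80 = 30.0 | 57.4% |

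**5. Check on the scan schedule**

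The simulation used 40,000 participants, scans every 8 weeks for the first 12 months and then every 12 weeks, 12 months of accrual and a cut at 48 months. Expected events per 50 participants fall from 34.5 to 32.8, 31.1, 29.3 and 27.4 at q = 5%, 10%, 15% and 20%. PFS at about 25 months rises from 48.6% to 50.4%, 52.4%, 54.4% and 56.6%. The median can fall only on a scan date, so it moves in 12-week steps: 24.8 months at q = 0, 27.6 at 5% and 10%, 30.4 at 15% and 20%.

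**6. The opposite disagreement**

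If the program calls PD one scan before the Investigator in 10% or 20% of participants, the median stays at 24.8 months and PFS at about 25 months falls from 48.6% to 48.3% or 47.8%. The one-scan lead is also an assumption; a longer lead would shift PFS further.

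**The case against.** The best defence is that the definitions have two parts, RECIST v1.1 and Investigator assessment, and that the program serves both. It reads only lesion data that the Investigator entered, including judgments on non-target progression and new lesions. Protocol Table 7 is itself a fixed mapping from those inputs to an overall response. Protocol 9.3.3.3 and 9.3.3.4 base the diagnosis of PD on RECIST v1.1, and an override on clinical judgment need not meet RECIST. The sentence in Protocol 8.1.1 follows one on images held for possible independent review, so it may only be choosing local over central reading. The SAP revision history suggests that the wording was deliberate, and a sensitivity analysis of overrides is planned.

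Much of this stands as a limit on size: with shared inputs, disagreement may be infrequent. It does not remove the conflict. SAP 4.10.2 itself separates the Investigator's determination from the program's and decides against the former, while 4.10.3.2 defines the event by the Investigator. Disagreement is also foreseeable: Protocol 8.1.1.1 treats starting or increasing a bisphosphonate or denosumab as indicating clinical progression unless progression is ruled out, and that is not a lesion entry. Even if such a call is not a RECIST PD, the SAP does not say how to handle a participant whose scans stopped because of it.

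**Conclusion.** The point holds as an inconsistency in the current text that can change reported results. For participants with Investigator-only PD and no later qualifying scan or death, the plan as written censors informatively and lengthens PFS and DOR.

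A reader might infer that PFS and DOR will be overstated overall. The documents do not support that. Overrides can go either way, an Investigator who overrides a programmed PD gives an earlier event under this rule, and neither rate nor net direction is stated. The medians of 26.7 and 30.0 months are upper approximations: q is assumed, all disagreement is put in one direction, every such case is censored, and the 24-month median is a study-duration assumption not split by line.

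A reader might also take the SAP's term primary evaluation to mean the trial's primary endpoint. It means the main analysis of secondary endpoints. The primary endpoint is the incidence of AEs and SAEs, and no hypothesis is tested. The correction belongs before database lock, but the primary objective does not depend on it.

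**What to change.** Use the Investigator's recorded RECIST v1.1 timepoint response as the main source for ORR, CBR, PFS, DOR and TTR. Make the program-derived response the sensitivity analysis for the same endpoints, add a concordance table by line of therapy, and query discordances before database lock.

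If the sponsor prefers to keep program precedence, it should align the definitions in SAP 3.2 and 4.10.3.2, declare the change in 4.13, and add a PFS and DOR sensitivity analysis that counts Investigator-only PD as an event on the date of the call.

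Either route is a change to SAP text and programming, with no new data. The downside of the preferred route is small: some Investigator calls may rest on clinical judgment and not strict RECIST, and the program-based sensitivity analysis would show how much that matters.

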Lerociclib is a substrate and inhibitor of P-gp and BCRP efflux transporters. Lerociclib exposure may be altered by concomitant use of drugs that are strong inhibitors or inducers of P-gp or BCRP.

- Monitor for adverse reactions when co-administering medications that are strong inhibitors of P-gp and BCRP.

Concomitant Radiotherapy and Surgery

Palliative radiotherapy may be permitted for the treatment of painful bony lesions provided that the lesions were known to be present at the time of study entry and the Investigator clearly documents that the need for palliative radiotherapy is not indicative of disease progression.

Approval from the Medical Monitor should be obtained prior to any surgery or start of alternative therapy that are not considered palliative.

Any diagnostic, therapeutic, or surgical procedures performed while the participant is receiving IMP (lerociclib) during the study period will be documented. Documentation will include information regarding the date(s), indication(s), description of the procedure(s), and any clinical or pathological findings.

Medications will be coded using the WHO Drug Dictionary.

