8.1.1.1. Lesions: Identification and Follow-up

Measurable Lesions

Measurable tumor lesions are defined as tumor lesions with an LD (measured in at least 1 dimension) with a minimum size as follows ([Eisenhauer 2009](#)):

- 10 mm by CT or MRI (with a scan slice thickness of no greater than 5 mm)

Measurable lymph nodes must be ≥ 15 mm on the short axis by CT or MRI (with a scan slice thickness of no greater than 5 mm); only the short axis is to be measured at baseline and follow-up.

Lytic bone lesions or mixed lytic-blastic lesions with a soft tissue component meeting the definition of measurability above can be considered measurable lesions.

Cystic lesions representing cystic metastases that meet the definition of measurability described above can be considered measurable lesions. If present, noncystic lesions should be selected as target lesions for this study.

A tumor lesion that has been previously irradiated may be considered measurable if unequivocal growth of the lesion has been demonstrated.

Target lesions: At baseline, up to 5 measurable tumor lesions/lymph nodes (with a maximum of 2 lesions per organ) should be identified as target lesions that will be followed to quantitate the status of disease during the study. Lesions with the LD, that are representative of all involved organs, and for which reproducible repeated measurements can be obtained should be selected as the target lesions.

At Screening and at each follow-up timepoint ([Table 1](#)), each target lesion should be measured and the overall tumor burden will be calculated as the sum of the diameters of the target lesions (LD for tumor lesions and short axis for lymph nodes) and documented in the eCRF. If a target lesion fragments into multiple smaller lesions, the LDs of all fragmented portions are added to the sum of the diameters. If multiple lesions coalesce, the LD of the coalesced lesion will be included in the sum of the diameters.

Nonmeasurable Lesions

Nonmeasurable lesions include tumor lesions with an LD < 10 mm, lymph nodes with ≥ 10 to < 15 mm short axis, or nonmeasurable lesions such as leptomeningeal disease, ascites, pleural or pericardial effusion, inflammatory breast disease, lymphangitic involvement of skin or lung, or abdominal masses/abdominal organomegaly identified by physical exam that is not measurable by CT scan or MRI ([Eisenhauer 2009](#)).

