8.1.1.2. Definitions of Tumor Response and Disease Progression

The determination of tumor response and progression will be based on the RECIST v1.1 criteria ([Eisenhauer 2009](#)). The definitions for tumor response per RECIST, v1.1 are provided below.

Evaluation of Target Lesion Response

- **Complete response:** Disappearance of all target lesions. Any pathological lymph nodes (whether target or nontarget) must have reduction in short axis to < 10 mm
- **Partial response:** At least a 30% decrease in the sum of diameters of target lesions, taking as reference the baseline sum of diameters
- **Progression of disease:** At least a 20% increase in the sum of diameters of target lesions, taking as reference the smallest sum on study (this includes the baseline sum if that is the smallest on study). In addition to the relative increase of 20%, the sum must also demonstrate an absolute increase of at least 5 mm. The appearance of 1 or more new lesions is also considered progression
- **Stable disease:** Neither sufficient shrinkage to qualify for PR nor sufficient increase to qualify for PD, taking as reference the smallest sum of diameters while on study

A response category of not evaluable is to be used when there is inadequate information to otherwise categorize the response status.

Evaluation of Nontarget Lesions

- **Complete response:** Disappearance of all nontarget lesions and normalization of tumor marker level. All lymph nodes must be < 10 mm short axis
- **Non-CR/Non-PD:** Persistence of 1 or more nontarget lesions and/or maintenance of tumor marker level above the normal limits
- **Progression of Disease:** Unequivocal progression of existing nontarget lesions or the appearance of at least 1 new lesion

Evaluation of Overall Response

[Table 7](#) describes the evaluation of overall response at each timepoint based on target and nontarget lesion responses at each timepoint, as well as the appearance of new lesions. The best overall response is the best response recorded from the start of the treatment until disease progression. Confirmation of CR and PR is required as previously described.

Table 7: Evaluation of Overall Response at Each Timepoint

| Target Lesions | Nontarget Lesions | New Lesions | Overall Response |
|----------------|-------------------|-------------|------------------|
| CR | CR | No | CR |
| CR | Non-CR/Non-PD | No | PR |
| CR | Not evaluated | No | PR |

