By-participant listings of prior and concomitant medications will be produced with ATC level 2 and preferred term, including actual non-imputed start/stop dates, route, dose, frequency, and indication (Analysis Set: Safety Analysis Set). When the indication is an AE or medical history, the medical history or AE identifier will be listed.

By-participant listings of prior and concomitant procedures will be produced with ATC level 2 and preferred term, including procedure date(s), site, type of procedure, if oncological in nature, and if used to treat target or non-target lesions.

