4.10.2.1 Confirmation of Response

Unless otherwise specified analyses of response will be based on confirmed response. Confirmation of an initial response (CR or PR) requires observation of an equal or better response, following adequate follow up time defined as ≥ 28 days, without intervening PD.

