4.10.3.4 Duration of Response (DOR)

Only participants who have a confirmed response will be included in the analysis of DOR. DOR is defined as the time to PFS Event from first confirmed response. DOR will start at the time of the initial response and not the time for the confirmatory scan.

The definition of the end of DOR is the same as PFS Event, and the censoring rules will be the same as shown in Table 2 above.

Descriptive summaries of time to event data will include median, twenty-fifth and seventy-fifth percentiles, and associated 2-sided 95% CIs based on Kaplan-Meier methods.

A Kaplan-Meier plot will be presented and will include the number of participants at risk over time by line of therapy. No formal statistical hypothesis will be tested.

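### In the visible text, response is cut off only at progression but PFS and DOR also at new antineoplastic therapy, so a confirmed response first seen after a switch of drug counts for lerociclib with a negative DOR

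*SAP*

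**What the plan says.** **Response endpoints.** SAP 4.10.2 states: "Once a RECIST v1.1 timepoint response of PD is observed all subsequent RECIST evaluations will not be used in analysis". The sentence goes on to allow for exceptions, and the text that follows is redacted; a second redaction closes the paragraph on the response-evaluable set. Protocol 8.1.1.2 sets the same window without redaction: "The best overall response is the best response recorded from the start of the treatment until disease progression". SAP 4.10.2.1 says that confirmation "requires observation of an equal or better response, following adequate follow up time defined as ≥ 28 days, without intervening PD". The definitions of ORR and CBR (SAP 4.10.3.1) and TTR (SAP 4.10.3.5) add no other cut-off.

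**PFS and DOR.** Table 2 in SAP 4.10.3.2 censors a participant who starts new antineoplastic therapy before PD or death, at the last tumour assessment on or before that start. For DOR, SAP 4.10.3.4 says "the censoring rules will be the same as shown in Table 2 above". It starts DOR at the initial response and does not require that response to precede a new therapy.

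**Scans after lerociclib stops.** The documents point both ways.
- The schedule of activities (Protocol 1.3) and Protocol 8.1.1 run tumour evaluation to progression. Neither lists a new therapy as a reason to stop. SAP 4.10.3.2 expects scans after the end of lerociclib and restricts their use for PFS only.
- The Protocol synopsis, Protocol 4.1 and SAP 3.1 describe imaging during lerociclib treatment. The tumour-evaluation windows in SAP 4.10.1.3 end at EOT/ED, 15 days after the last dose.

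**The concern.** Two sets of endpoints computed from the same scans have different end points. PFS and the end of DOR stop at a switch of drug; best response, ORR, CBR and TTR do not. A participant who leaves lerociclib for toxicity, starts another anticancer drug and then responds would be credited to lerociclib. The DOR rule would close that response before it opened. A negative time cannot enter a Kaplan-Meier estimate, so the programmer would have to drop or reset it without a stated rule.

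Best response is the highest category over the scans used (SAP 4.10.3.1). Extra scans before PD can therefore leave ORR and CBR unchanged or raise them, but cannot lower them. The study has one arm, so no control group offsets this. The same open window applies to the best percentage change in the waterfall plot.

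**Working it through.** **1. The plan's own figure.** Protocol 9.4 and SAP 4.12 plan 50 participants per line, 80% with measurable disease: 50 × 0.80 = 40. The largest 95% half-width at n = 40 is 1.96 × √(0.25/40) = 15.5% by the normal approximation, and 16.2% by Clopper-Pearson at 20/40. Both agree with the stated figure of about 16%, so n = 40 is used below.

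**2. Date rules.**
- Scans every 8 weeks from day 1 fall on days 57, 113, 169, 225 and 281. SAP 4.10.1.3 centres the first window, days 50 to 64, on day 57.
- Censoring date under Table 2: last scan on or before the new therapy.
- Duration: end − start + 1. The SAP gives this formula for PFS; applying it to DOR is an assumption.

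**3. Participants who switch without PD.**

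| Case | New therapy | First PR | Confirmed | Censored | DOR (days) |
|---|---|---|---|---|---|
| A: SD on days 57 and 113 | day 130 | day 169 | day 225 | day 113 | 113 − 169 + 1 = −55 |
| B: early switch | day 60 | day 169 | day 225 | day 57 | 57 − 169 + 1 = −111 |
| C: PR before the switch, confirmed after it | day 130 | day 113 | day 169 | day 113 | 113 − 113 + 1 = 1 |

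In case A the confirmation gap is 225 − 169 = 56 days, above the required 28. As written, A is a confirmed responder with TTR 169 − 1 + 1 = 169 days. With a cut at day 130, A is a non-responder with no TTR or DOR. Case C counts as a response only because of a scan on the new drug, but its DOR is not negative.

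**4. CBR.** SAP 4.10.3.1 requires SD for at least 24 weeks, plus or minus 7 days, so at least 168 − 7 = 161 days. The start of the count is not stated; first dose is assumed. Take SD on days 57 and 113, a switch on day 130 and SD on day 169.
- Before the switch: 113 − 1 = 112 days (16 weeks), short of 161.
- With the one post-switch scan: 169 − 1 = 168 days (24 weeks), which qualifies. SD needs no confirmation.

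Protocol 9.3.3.2 instead asks for 8 weeks. This participant would meet that on day 57 (57 − 1 = 56 days), before the switch, so the CBR effect described here depends on the SAP's 24-week rule.

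**5. Size.** One participant is 1/40 = 2.5 points. For illustration, assume 16 true responders of 40:

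| Post-switch responders added | ORR | Exact 95% CI |
|---|---|---|
| 0 | 16/40 = 40.0% | 24.9 to 56.7 |
| 2 | 18/40 = 45.0% | 29.3 to 61.5 |
| 4 | 20/40 = 50.0% | 33.8 to 66.2 |

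The base of 16 and the range of 0 to 4 are assumptions; neither document supplies them.

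**The case against.** **Redaction.** SAP 4.10.2 is blacked out just where a further rule could stand. This limits the claim to the visible text. The position of the first gap suggests exceptions to the post-PD exclusion, but another rule cannot be ruled out. Protocol 8.1.1.2 and SAP 4.10.2.1 are not redacted and name progression alone.

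**Few scans may exist.** Several passages tie imaging to treatment or EOT/ED, and Protocol 7.1.1 gives a participant who stops for reasons other than PD one scan if none was done in the prior 4 weeks. If sites follow these, cases will be rare. But Protocol 7.1.1 also encourages completion of all scheduled assessments, and the schedule of activities runs them to progression. This is an inconsistency to reconcile and does not act as an analysis cut-off.

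**Any shrinkage after a switch counts.** A reader might infer this, but it is too strong. A first response after the switch needs two scans at least 28 days apart, so a single EOT scan cannot create one. CBR through SD has no such protection.

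**Another drug taken alongside lerociclib.** Also not supported: Protocol 6.9 bars other anticancer therapy before progression while lerociclib is being taken, and starting one ends study therapy (Protocol 4.1). Only scans after discontinuation are at issue.

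**Radiotherapy or surgery to a target lesion.** A reader might extend the negative DOR to these. Protocol 6.9 says "Palliative radiotherapy may be permitted for the treatment of painful bony lesions", and Protocol 8.1.1.1 lets some bone lesions be measurable ("Lytic bone lesions or mixed lytic-blastic lesions with a soft tissue component"). The case is narrow: the lesion must be painful, known at entry, have a measurable soft-tissue part and be a chosen target. It does not by itself give a negative DOR. Radiotherapy on day 130, PR on day 169 and PD on day 281 give 281 − 169 + 1 = 113 days. A negative value would need the procedure to be classed as new antineoplastic therapy, and the SAP does not define that term.

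**Low stakes.** ORR is a secondary, descriptive endpoint and the primary endpoint is adverse events. This lowers the priority but does not remove the inconsistency.

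**Conclusion.** The point holds for new anticancer therapy. Followed as written, the visible rules count a confirmed response, or a 24-week SD, first reached after a switch of drug as a lerociclib result. For a first response after the switch they also give a negative DOR (−55 days in case A). This rests on three conditions: no contrary rule in the redacted text, at least some scans after lerociclib stops and before PD, and the PFS duration formula applied to DOR.

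Each case is worth 2.5 points of ORR or CBR per line. The number of cases is unknown, so the total effect may be nil. Local treatment of target lesions remains a minor secondary point.

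**What to change.** In SAP 4.10.2, 4.10.2.1, 4.10.3.1 and 4.10.3.5, and in Protocol 8.1.1.2, state that only tumour assessments on or before the earliest of PD, start of subsequent antineoplastic therapy or data cut are used. Apply this to best overall response, confirmation, ORR, CBR, TTR, the start of DOR and best percentage change, so that all match Table 2. If the redacted text already says this, align the unredacted sections with it.

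Reconcile the passages on imaging after lerociclib stops: the Protocol synopsis, 1.3, 4.1, 7.1.1 and 8.1.1, and SAP 3.1, 4.10.1.3 and 4.10.3.2.

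For local treatment, at most flag the participants from the SAP 4.7 procedure listing, which records whether a procedure was "if oncological in nature, and if used to treat target or non-target lesions", and report a sensitivity analysis. That field may not identify which lesion was treated, so it cannot be relied on for a lesion-level rule.

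The cost is a few sentences and a few lines of programming. New anticancer therapies are already collected, and SAP 6.2 already has a rule for partial start dates. The downside is that ORR and CBR may be slightly lower.
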